MRI	Magnetic Resonance Imaging					
MSDS	Material Safety Data Sheet					
NIH	National Institutes of Health					
OHRP	Office for Human Research Protections					
PET	Positron Emission Tomography					
PI	Principal Investigator					
PTV	Planning Target Volume					
QA	Quality Assurance					
QC	Quality Control					
RSI	Radiosensitivity Index					
RT	Radiation Therapy					
SAE	Serious Adverse Event					
SAP	Statistical Analysis Plan					
SMC	Safety Monitoring Committee					
SOP	Standard Operating Procedure					
UP	Unanticipated Problem					
L						

Version 2.3 09 Jul 2021

#### STUDY SUMMARY

- Title:Use of a Proliferation Saturation Index to Determine Personalized
Radiotherapy Fractionation for Patients with HPV+ Oropharyngeal
Cancers.
- *Précis:* We will use a mathematical model for each HPV+ oropharyngeal cancer patient's tumor growth characteristics to select radiotherapy fractionation. We believe it will most likely to result in a rapid response by week 4 of treatment.

#### **Objectives:**

**Primary Objective:** 

We hypothesize that by using individual patient proliferation saturation index (PSI) to select radiotherapy fractionation (conventional fractionation or hyperfractionation) to improve the likelihood of a rapid response (defined as  $\geq$  32% reduction in volume at 4 weeks).

### **Secondary Objectives:**

- Rate of complete response by CT at 2 months or PET/CT at 3 months following completion of therapy.
- Correlate response and outcome to pre-treatment and during treatment radiomics features on PET/CT/MRI.
- Correlate response and outcome to mathematical models of tumor growth and death dynamics pre-treatment and during treatment.

#### **Exploratory Objectives:**

 Identify potential biomarkers of response to adaptive radiation therapy based on evaluation of tumor immune microenvironment and detection of HPV DNA in oral gargles and plasma.

#### Endpoint

**Primary Endpoint:** For patients with HPV+ squamous cancer of the oropharynx, fractionation of radiation will be individualized based on their PSI. Response will be measured after 4 weeks of RT as assessed by CT or MRI, as described in section 10.0. Primary objective is to increase the rate of response of  $\geq$  32% at 4 weeks to 63% of patients, above the expected 49%.

[figure not shown]
Population:	Total sample size of 60 patients, which will include men and women $\geq$ 18 years with pathologically (histologically or cytologically) proven diagnosis of HPV+ squamous cell carcinoma of the oropharynx and no evidence of distant metastases. This is a single center study
Phase:	2

Number of Sites 1 enrolling participants:

Study Duration:	~30 months		
Agent :	Proliferation Saturation Index – a measure of the carrying capacity of the patient for the tumor burden. We will use this to select radiotherapy fractionation.		
Description of Study			

Participant Duration: ~33 months

#### 2 INTRODUCTION: BACKGROUND INFORMATION AND SCIENTIFIC RATIONALE

# 2.1 BACKGROUND INFORMATION

[figure not shown]
With increasing understanding of the complexity of tumor heterogeneity, it would be reasonable to hypothesize that cancer therapy should be tailored to individual patients, which is the central principle underlying precision medicine. Currently in radiation medicine, decisions for total dose and fractionation are based empirically on clinical data, albeit often from randomized trials. Current efforts in radiation oncology to personalize radiation therapy mainly address adapting the target volume based on response. However, there have been no trials attempting to individualize total dose and fractionation. Here we provide one of the first clinical studies to deliver personalized radiation fractionation dose therapy for cancer.

# 2.2 PROLIFERATION SATURATION INDEX

Tumors are composites of proliferating and growth arrested cells. Overall radiation response depends on their respective proportions at irradiation. In multi-compartment mathematical models that distinguish between proliferating and growth-arrested cells, we have shown that proliferation and oxygenation status-dependent radiation response can be simulated on the cellular level. Tumor growth in vivo can be approximated by logistic dynamics. Initial exponential growth at low cell densities when most cells have access to ample resources decelerates when cells at the core of the tumor become growth-arrested, mainly due to limited space and exhausted intratumoral nutrient supply as resources are consumed by cells closer to the tumor surface. This established the notion of a tumor carrying capacity (K) as the maximum tumor volume that can be supported by a given environment. The tumor carrying capacity is patient-specific, depending on the established oxygen and nutrients supply through tissue vascularization, removal of metabolic waste products, and evasion of immune surveillance. Hence, the tumor volume-to-carrying capacity ratio (V/K) describes the saturation in overall tumor cell proliferation as the tumor approaches its carrying capacity, which we call a Proliferation Saturation Index (PSI). Logistic

growth is modeled as  $dt = T_{POT}$  (eqn. 1), where V is the tumor volume at time t, dV/dt is the change of tumor volume over time TPOT is the intrinsic potential doubling time.

Radiation response is modeled as instantaneous volume changes  $V_{postIR} = V - \gamma_d V(1 - PSI)$  (eqn. 2)

**Figure 1. A)** Two patients with identical tumor volume but different PSI at treatment begin (day 0) exhibit different reduction in tumor volume after fractionated RT. **B**) Logistic tumor growth and radiation response model predicted curves (*eqns.* 1+2; solid black lines) to four lung cancer patientsdata (red circles) with growth rate  $ln2/T_{POT}=0.045$  and radiation-induced death  $\gamma_{2Gy}=0.084$ , and patient-specific carrying capacities Ki. PSIi: Proliferation Saturation Index for patient Pi at first treatment (t=0).

at irradiation moments, where  $\gamma_d = 1 - e^{-(\alpha d + \beta d^2)}$  represents radiation-induced death after dose d following the linear-quadratic model. It follows from (eqns. 1+2) that larger PSI reflect a low proliferating cell fraction and, thus, treatment refractory tumors, whereas tumors with low PSI are more proliferative and radiosensitive. As such, two patients that present with similar tumor volume could have a different tumor growth history and thus a different PSI, which results in different responses to the same radiotherapy protocol (Fig. 1A). In a preliminary study of non-small cell lung cancer and head and neck cancer patients we have confirmed that PSI varies greatly between patients (0.26±0.33; [0.03-0.75]) and correlates inversely with radiotherapy response. A patient-specific pretreatment PSI was sufficient to fit individual patient response data (r=0.98; Fig. 1B).

# 2.3 RADIOTHERAPY IN HEAD AND NECK CANCER

Radiotherapy as definitive treatment for oropharyngeal cancer is a standard of care. Based on multiple clinical trials, standard doses are in the range of 60 - 70 Gy at 2 Gy given once daily or 60 - 81.6 Gy given twice daily. However, to date the selection of fractionation has been empiric in nature. We hypothesize that head and neck cancer represents an ideal opportunity to establish a paradigm of individualized radiotherapy dosing based on mathematical models.

[figure not shown]
We are specifically selecting HPV+ oropharyngeal cancer patients because at an early stage (AJCC 8th edition stage T1-2 N0-1 with limited lymph node involvement), radiotherapy alone is a standard of care, reducing the variables in question. For example, RTOG H0022 treated patients with up to radiographic T1-2 N0-1 (AJCC 7th edition T1-2 N0-2a) oropharyngeal tumors with radiotherapy alone, with locoregional control rates of >90%. Additionally, multiple retrospective reports from large institutions such as MD Anderson and Princess Margaret demonstrate >90% locoregional control rates for oropharyngeal cancer patients with T1-2 N0-2b (AJCC 7th edition).

[figure not shown]
However, RTOG 1016, which treated patients with locoregionally advanced HPV+ oropharyngeal cancer with 70 Gy of radiotherapy and either cisplatin or cetuximab was recently published. This demonstrated the superiority of cisplatin over cetuximab in combination with radiotherapy. RTOG 1016 included overlapping patient population that is eligible for the current trial, specifically patients with a single lymph node > 3 cm or multiple lymph nodes in ipisilateral neck. Examination of Forrest

plots from the trial suggests that patients with a > 10 pack year history of cigarette smoking were at higher risk and had a greater benefit from cisplatin. We therefore will exclude patients who are locoregionally advanced with a significant smoking history.

Additionally, recent review of Moffitt Cancer Center internal data suggests that patients with greater than 5 positive lymph nodes are at a higher risk of regional failure, with locoregional control at 3 years of 94.9% for 1-5 lymph nodes vs 80.1% for > 5 lymph nodes (p = 0.001). By restricting patients to T1-2 N0-1 with 5 or less lymph nodes and a smoking history of 10 pack years or less, 3-year locoregional control of patients treated with radiation alone at Moffitt Cancer Center was 94.7% (n=81) compared to 95.9% with concurrent radiotherapy and systemic therapy (n=98) (personal communication [name]).

In a retrospective analysis of 44 patients, decrease in nodal size of  $\geq$  40% was associated with a locoregional control (LRC) of 100% at 2 years, compared with 78% for a decrease of < 40%. Retrospective review of a Moffitt cohort (n=49) suggests that a cut point of 32% reduction resulted in 100% LRC and DFS (Figure 2A&B). Of note, half of these patients were treated with radiation alone.

In the mathematical modeling of radiation treatment response, there is a suggestion of a more robust treatment response by hyperfractionation when the PSI is > 0.75 (Figure 3).

[figure not shown]

Figure 3: Model of tumor response at 4 weeks by initial pretreatment PSI.

We therefore hypothesize that by personalizing the fractionation, we will increase the number of patients achieving a 32% reduction by week 4.

# 2.4 RATIONALE FOR FRACTIONATION SCHEMES USED IN THIS STUDY

All fractionation schemes are selected are standards of care in H&N cancer. For example, RTOG 7913 established that the locoregional control rates between these two total dose and fractionation schemes were equivalent.

#### 2.5 RATIONALE FOR BIOMARKER STUDIES

#### 2.5.1 EVALUATION OF TUMOR IMMUNE MICROENVIRONMENT (TIM)

The interplay between the tumor and its TIM is critical in tumor formation, metastasis, and clinical outcomes including radiation therapy response. Characterization of lymphoid and myeloid immune cells has shown to be prognostic in HNSCC, but their association with radiation therapy benefits has not been clearly evaluated. Significance of the TIM in context of the PSI in HNSCC is entirely unknown. The findings from this innovative and highly interdisciplinary project will have a significant clinical impact in improving the selection of patients who will gain the most benefit from receiving PSI based radiation therapy, offering further biological insight to the mechanisms of resistance, and subsequently developing optimal combination therapies for immune modulating agents.

#### 2.5.2 EVALUATION OF HPV DNA VIRAL LOAD IN ORAL GARGLES AND PLASMA

Detection of HPV DNA in oral gargles and plasma after the completion of treatments has shown to associate with recurrence. In a study by Ahn, et al, HPV-16 E6 and E7 DNA were determined from plasma and/or saliva samples obtained before and after treatments in 93 patients. Patients with detectable HPV DNA in the posttreatment saliva and either saliva or plasma had reduced overall survival. However, significance of persistent HPV DNA detection in saliva and/or plasma in context of the PSI in HNSCC is entirely unknown. Evaluation of HPV DNA as a predictive biomarker of PSI-based radiation therapy warrants further studies.

# 2.6 POTENTIAL RISKS AND BENEFITS

#### 2.6. KNOWN POTENTIAL

As all interventions are considered standards of care, no additional potential risks would be incurred.

#### 2.6.2 KNOWN POTENTIAL BENEFITS

By selecting the most ideal fractionation scheme, we may be able to improve the 4 week response rate which has been associated with improved locoregional control.

#### **3 OBJECTIVES AND PURPOSE**

#### 3.1 PRIMARY OBJECTIVE

For patients with HPV+ squamous cancer of the oropharynx, fractionation of radiation will be individualized based on their PSI. Response will be measured after 20 days of RT as assessed by CT or MRI, as described in section 10.0. Primary objective is to increase the rate of response of  $\geq$  32% at 20 days to 63% of patients, above the expected 49%.

#### **3.2 SECONDARY OBJECTIVES**

- Rate of complete response by CT at 2 months or PET/CT at 3 months following completion of therapy.
- Correlate response and outcome to pre-treatment and during treatment radiomics features on PET/CT/MRI.
- Correlate response and outcome to mathematical models of tumor growth and death dynamics pre-treatment and during treatment.
- Correlate RSI/GARD with mid-treatment and post-treatment response.
- Correlate clearance of HPV in serum/oral gargle specimens with mid-treatment and posttreatment response.

## **3.3 EXPLORATORY OBJECTIVES**

 Identify potential biomarkers of response to adaptive radiation therapy based on evaluation of tumor immune microenvironment and detection of HPV DNA in oral gargles and plasma.

# 4 STUDY DESIGN AND ENDPOINTS

# 4.1 DESCRIPTION OF THE STUDY DESIGN

 $PSI = \frac{V_{diagnosis} \times e^{\lambda \ \Delta t} - V_{treatment}}{V_{diagnosis} \times (e^{\lambda \ \Delta t} - 1)}$ 

- PSI will be calculated according the above formula, where Vdiagnosis is the volume of the tumor at first imaging and Vtreatment is the volume of the tumor at second pretreatment imaging, t is time, and λ is doubling time. Patients with a PSI ≤ 0.75 will be assigned to conventional fractionation group, and PSI > 0.75 will be assigned to the hyperfractionation group (Figure 3).
- Each site of disease (primary and each lymph node) will be independently contoured and PSI calculated for each. PSI of the lymph nodes will take priority over primary site. PSI of the largest lymph node will take priority over smaller lymph nodes.
- Based on PSI, patients will be assigned to one of two cohorts:
- $PSI \leq 0.75$ : Conventional fractionation 2 Gy once daily, Monday through Friday.
- \*\*Should patients be assigned to conventional fractionation, and do not meet the predicted >32% reduction AND they are not receiving concurrent chemotherapy, their treatment will be accelerated via a 6th fraction per week, given as a BID dose once during the week or on a Saturday.
- PSI > 0.75: Hyperfractionation 1.2 Gy twice daily, at least 6 hours apart, Monday through Friday.

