4.2.1 On Treatment response at 4 weeks during RT

Week 4 CT and/or MRI will be loaded into the treatment planning system or other software for volumetric evaluation of tumor size. This will be compared against CT simulation or week 1 CT/CBCT and/or MRI, whichever is larger. The percent response will be calculated.

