#### 5.1 PARTICIPANT INCLUSION CRITERIA

In order to be eligible to participate in this study, an individual must meet all of the following criteria:

- Provision of signed and dated informed consent form
- Stated willingness to comply with all study procedures and availability for the duration of the study
- Male or female, aged  $\geq$  18 years
- Pathologically (histologically or cytologically) proven diagnosis of p16+ or HPV+ squamous cell carcinoma (including the histological variants papillary squamous cell carcinoma and basaloid squamous cell carcinoma) of the oropharynx; cytologic diagnosis from a cervical lymph node is sufficient. Patients with unknown primary (T0) should be both p16 and HPV positive. Clinical evidence should be documented, and may consist of pathology, palpation, imaging, or endoscopic evaluation, and should be sufficient to estimate the size of the primary (for T stage).
- AJCC 8th edition staging T0-2 N0-1 M0 (N1 includes clinical tumor involvement in only 1-5 lymph nodes) Patients with any smoking history are included if N0 or a single involved node size ≤3cm. However, if the number of involved lymph node is ≥2 or any lymph node size >3 cm, only patients with ≤ 10 pack years of smoking is eligible.
- Patients must have clinically or radiographically evident measurable disease at the primary site or at nodal stations.
- CT or MRI performed at least 1 week apart. This can consist of diagnostic imaging and radiation therapy planning imaging.
- No evidence of distant metastases
- ECOG Performance Status 0 to 2

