# 7 STUDY PROCEDURES AND SCHEDULE

#### 7.1 STUDY PROCEDURES/EVALUATIONS

 $PSI = \frac{V_{diagnosis} \times e^{\lambda \Delta t} - V_{treatment}}{V_{diagnosis} \times (e^{\lambda \Delta t} - 1)}$ 

PSI will be calculated according the above formula, where Vdiagnosis is the volume of the tumor at first imaging and Vtreatment is the volume of the tumor at second pretreatment imaging, t is time, and  $\lambda$  is doubling time. Each site of disease will be contoured individually, and PSI calculated. PSI of lymph nodes will have priority over primary site. PSI of the largest lymph node will have priority over smaller lymph nodes. Patients with a PSI  $\leq$  0.75 will be assigned to conventional fractionation group, and PSI > 0.75 will be assigned to the hyperfractionation group (Figure 3).

- Medical history within 90 days of start of treatment, including history, focused physical exam of the head and neck, assessment of performance status, and weight.
- Imaging will consist of pre-treatment CT and/or MRI, with at least 2 exams one week apart. Pre-treatment PET/CT while ideal, is not required. On first day of RT (or within 5 days of starting RT), CT simulation will be repeated. During week 4 of radiotherapy (~fraction 20 for conventionally fractionated patients or ~fraction 40 for hyperfractionation patients, CT simulation and MRI will be repeated. At ~8 weeks after treatment is complete CT of neck or ~12 weeks PET/CT will be performed for response assessment.

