fBlood samples to be collected at pre-therapy, during treatment at week 2 and week 4, end of treatment, 3 months post-RT, 6 months post-RT, 12 months post-RT, 18 months post-RT, 24 months post-RT, time of diseaseprogression (if sooner than 24 months), and end of study (if patient discontinues the study with any reason sooner than 24 months). See 7.2.4/7.2.5 for collection windows.

gFollowing this visit, patients are considered off the trial and are followed as per standard of care. hPre-treatment CT or MRI for PSI calculation can be up to 180 days prior to CT simulation.

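### The planning CT may supply both the second PSI volume and the week-4 baseline, so its contouring error biases secondary PSI-response associations in the negative direction

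*Combined protocol and SAP*

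**What the plan says.** Sections 4.1 and 7.1 compute PSI from two pre-treatment volumes, where "Vtreatment is the volume of the tumor at second pretreatment imaging". Section 5.1 asks for "CT or MRI performed at least 1 week apart" and adds "This can consist of diagnostic imaging and radiation therapy planning imaging". A footnote to the 7.3 schedule dates the PSI imaging relative to simulation: "Pre-treatment CT or MRI for PSI calculation can be up to 180 days prior to CT simulation". The planning CT is therefore a permitted second PSI image, though not a required one.

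For week-4 response, 4.2.1 states the baseline: "This will be compared against CT simulation or week 1 CT/CBCT and/or MRI, whichever is larger". Section 7.1 adds a further scan: "On first day of RT (or within 5 days of starting RT), CT simulation will be repeated". I read the CT simulation in 4.2.1 as the planning scan, because it is listed apart from week-1 imaging and 7.1 speaks of repeating it.

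The analysis exposed is the secondary objective in 3.2: "Correlate response and outcome to mathematical models of tumor growth and death dynamics pre-treatment and during treatment". Section 10.1 assigns it to logistic regression. Section 10.2.3 says the models will be built from volumes on the various scans and validated by their correlation with response and outcome. Neither section names PSI as a predictor, although PSI is the pre-treatment growth index that 2.2 defines. Nothing in the plan requires the PSI scan and the response baseline to be different scans.

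**The concern.** A measured volume that enters two derived quantities carries its error into both. Here the signs are opposite. An over-contoured planning CT gives a low PSI and a large apparent reduction; an under-contoured one gives a high PSI and, where that scan is the baseline, a small reduction. Two quantities that are truly unrelated then show a negative association.

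Section 2.2 reports from preliminary work that PSI is inversely related to radiotherapy response. The artefact points the same way, so a negative association in this trial could be taken as validation of the model under 10.2.3 when part of it is shared contouring error.

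**Working it through.** **The plan's own figure.** The documents give no figure for this coupling. The figure they do give, for the primary design, reproduces. Rejection probability = P(X1 >= 30) + sum over k = 28, 29 of P(X1 = k) x P(X2 >= 35 - k), with X1 binomial on 49 patients and X2 on 11. At a rate of 0.63 this is 79.1% (stated: about 79%). At 0.49 it is 0.0928 (stated type I error: 0.1). PSI does not appear in this calculation.

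**Inputs.**
- From the documents: the PSI formula and the 0.75 cut (4.1); the larger-of-two baseline (4.2.1); a scan gap of at least 7 days (5.1) and up to 180 days before simulation (7.3); N = 60.
- Assumed: growth rate 0.045 per day. This is the lung-cancer fit in 2.2, "ln2/T_{POT}=0.045"; no value is given for this trial.
- Assumed, with no figure in the documents: contouring error, its independence between scans, the spread of true shrinkage, the distribution of PSI in this population, and use of the same lesion for PSI and response.

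**Signs.** PSI = (Vd x g - Vt) / (Vd x (g - 1)), with g = exp(lambda x gap). Hence dPSI/dVt = -1 / (Vd x (g - 1)), which is negative. Shrinkage = 1 - V4/Vbase, so d(shrinkage)/dVbase = V4/Vbase^2, which is positive.

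**One patient.** Take a 7-day gap, true PSI 0.75 and Vd = 1.
- g = exp(0.315) = 1.370, so true Vt = 1.370 - 0.75 x 0.370 = 1.093.
- A +10% error gives Vt = 1.202 and PSI = (1.370 - 1.202)/0.370 = 0.45, a shift of about -0.30. The shift is -0.14 at 14 days, -0.06 at 28 and -0.03 at 60.
- If that scan is the baseline, a true 32% reduction reads as 1 - 0.68/1.10 = 38%.
- With a -10% error PSI rises by the same 0.30. If the week-1 volume is correct it is now the larger, and shrinkage still reads 32%. The larger-of-two rule thus passes the error on in only one direction, which is why it roughly halves the effect.

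**Simulation with shrinkage truly independent of PSI.** Mean PSI-shrinkage correlation at error CV 10%, true shrinkage SD 20 points, PSI mean 0.7 and SD 0.2:

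| Gap (days) | Planning CT only | Larger of two (the plan) | Start-of-RT scan not in PSI |
|---|---|---|---|
| 7 | -0.20 | -0.10 | 0.00 |
| 14 | -0.16 | -0.08 | 0.00 |
| 28 | -0.10 | -0.05 | 0.00 |
| 60 | -0.06 | -0.03 | 0.00 |

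With n = 60, a two-sided 5% test needs |r| >= 2.002/sqrt(58 + 2.002^2) = 0.254. Under the plan's rule and these inputs, the chance of a falsely significant negative correlation (nominal 2.5%) is about 12% at 7 days and 6% at 28 days. With the start-of-RT scan it is 2-3%.

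**Other assumed inputs.** With PSI uniform on 0.03-0.97, SD of the log volume ratio 0.30 and log-volume error SD 5-15%, the larger-of-two rule gives Spearman about -0.01 to -0.13. Two-sided false positives are about 5-17% at nominal 5%. For gaps of 60-180 days, at error SD 10-15%, Spearman is -0.02 to -0.05 and a score test of binary response rejects in 4-6% of trials. At the unfavourable end (error CV 20%, shrinkage SD 10 points, 7 days), r is -0.23 and the one-directional rate is 45% against 2.5%. In every setting the separate baseline returns the correlation to zero within simulation error.

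**The case against.** The strongest reply has five parts.

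1. **The overlap is permitted, not required.** This stands. The figures assume it occurs in every patient and are to that extent an upper case.
2. **The inputs are not the trial's.** This stands too. The gap may be long, and the bias then nearly vanishes. Error shared across a patient's scans cancels in both ratios: with half the error variance shared, Spearman at 7-28 days falls to -0.02 to -0.10. PSI comes from one prioritised lesion, while 4.2.1 does not say which lesions make up tumor size; summing lesions would dilute the coupling.
3. **No listed analysis names PSI, and no alpha is set for the secondary analyses.** Correct. The 5% level is a yardstick supplied here. The objective on growth models is still the natural place for PSI, and 10.2.3 treats correlation with response as validation.
4. **A reader might infer that contouring error creates the result the trial is designed to show, or tilts the trial towards its hypothesis.** The documents do not support that. The inverse relation is a preliminary finding in 2.2. The trial's hypothesis is a pooled rate of 63% against 49%. No PSI-group comparison appears in section 10. If one were made, the artefact would lower apparent response in the PSI > 0.75 group, against the hyperfractionation rationale in 2.3.
5. **A reader might also quote false-positive rates of 10-50%.** Those assume the planning CT as sole baseline, which is not the rule in 4.2.1.

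None of this removes the coupling. It limits its size and reach.

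**Conclusion.** The point holds as a bias in secondary analyses. Where the planning CT supplies both Vtreatment and the baseline, any association of PSI, or a PSI-based pre-treatment model, with week-4 response is pushed negative by measurement error alone. Under the plan's baseline rule the artefact is small to moderate: Spearman about -0.01 to -0.13, with false positives about 5-17% at nominal 5%. It is worst near the 7-day minimum gap and close to nominal from 60 days. These figures rest on lambda 0.045 per day, independent log-volume errors of 5-15% and the same lesion in both measures; larger error would make it worse, and shared error or summed lesions would make it smaller.

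The mechanism does not shift the pooled primary rate. Taking the larger of two noisy baselines can raise that rate, but that effect does not involve PSI and is a separate matter.

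**What to change.** In 10.1 and 10.2.3, state that every analysis relating PSI or a PSI-based model to week-4 response takes the start-of-RT scan as its baseline: the repeat CT simulation, or the day-1 CT or MRI actually obtained. State also that a scan used to compute PSI is never the baseline in those analyses. Report the same analysis with the larger-of-two baseline alongside as a sensitivity analysis. Leave the primary endpoint definition unchanged.

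The cost is analysis wording. The start-of-RT scan is already scheduled in 7.1 and 7.3, and a volume from early imaging is already needed to decide which baseline is larger. The schedule allows CT or MRI at that visit, which is why the wording should refer to the scan actually obtained. The downside is a second week-4 response measure, confined to these secondary analyses, which must be labelled so that it is not confused with the primary endpoint.

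### The PSI formula that assigns fractionation labels λ as a doubling time, but it is correct only if λ is the growth rate ln2/T_POT

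*Combined protocol and SAP*

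**What the plan says.** Section 4.1 gives the formula `PSI = (V_diagnosis·e^{λΔt} − V_treatment) / (V_diagnosis·(e^{λΔt} − 1))`. The two volumes come from the first and second pre-treatment scans. The symbols in the exponent are explained as "t is time, and λ is doubling time". Section 7.1 repeats the formula with the same label: λ "is doubling time. Each site of disease will be contoured individually, and PSI calculated". In both sections a PSI of 0.75 or less leads to conventional fractionation and a PSI above 0.75 to hyperfractionation.

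Section 2.2 supplies the model. PSI is V/K, tumour volume over carrying capacity, under logistic growth. The doubling time has its own symbol there: "TPOT is the intrinsic potential doubling time". The Figure 1 legend gives the growth rate as ln2/T_POT, with the value 0.045 for lung cancer data and no unit. Section 2.2 also reports preliminary PSI values between 0.03 and 0.75.

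For the interval between scans, section 5.1 requires "CT or MRI performed at least 1 week apart". Section 7.3, footnote h, allows the pre-treatment scan to be up to 180 days before CT simulation.

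**The concern.** A doubling time and a growth rate are inversely related, and section 2.2 keeps them apart. The exponent λΔt must be a pure number. A rate times a time is one; a doubling time times a time is a time squared, so the answer would change with the unit chosen.

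The formula is the intervention: it alone determines each patient's schedule. Someone who computes PSI from section 4.1 or 7.1 as written, or who audits or replicates an assignment from that text, would get values that do not measure V/K and could place patients on the wrong side of 0.75.

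**Working it through.** **Which λ the formula needs.** Write V0 for V_diagnosis, Vt for V_treatment and E = e^{λΔt}. Logistic growth with rate λ is dV/dt = λV(1 − V/K), with solution

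Vt = K·V0·E / (K + V0(E − 1)).

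Multiply out and divide by K: Vt + Vt·V0(E − 1)/K = V0·E. Hence

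Vt/K = (V0·E − Vt) / (V0(E − 1)),

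which is the printed formula, with λ the growth rate. Equation 1 is not fully legible in the copy reviewed, but the text of section 2.2 and the Figure 1 legend (rate = ln2/T_POT) are enough.

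For a growing tumour no other λ works. The derivative of the formula with respect to E is (Vt − V0)/(V0(E − 1)²), which is positive, so only one λ returns Vt/K.

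**Numerical check with λ as a rate.**
- V0 = 1, K = 1.5, λ = 0.045, Δt = 7: Vt = 1.0990; formula 0.7327; Vt/K = 0.7327.
- V0 = 1, K = 2, λ = 0.02, Δt = 28: Vt = 1.2729; formula 0.6365; Vt/K = 0.6365.

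**Literal reading, time in days (assumption).** With r = Vt/V0 and x = λΔt, the formula becomes PSI = 1 − (r − 1)/(e^x − 1). Take a doubling time of 1 day, the minimum gap of 7 days and r = 2. Then x = 7 and PSI = 1 − 1/(e^7 − 1) = 0.9991. A longer doubling time, a longer gap or a smaller r moves PSI closer to 1, or above 1 if the tumour shrank. This bound needs no particular value of λ.

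**Side by side.** Reading 0.045 as per day (assumption), T_POT = ln2/0.045 = 15.40 days. At 7 days the literal exponent is 15.40 × 7 = 107.8; the rate gives 0.045 × 7 = 0.315. The volume ratios are illustrative.

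| Volume ratio, gap | λ = 0.045 per day | λ = 15.40 (literal) |
|---|---|---|
| 1.10, 7 days | 0.730, conventional | 1.000, hyperfractionation |
| 2.0, 28 days | 0.604, conventional | 1.000, hyperfractionation |

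For PSI to be 0.75 or less, r must be at least 0.25·e^x + 0.75. Over 7 days that is 1.09-fold growth with the rate and about 10^46-fold under the literal reading. The latter therefore cannot return the preliminary range of section 2.2 for any plausible volumes.

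**Dependence on the unit.** For a true PSI of 0.50, a 14-day gap and T_POT of 15.4 days, the literal formula gives 1.000 in days, 0.995 in weeks and −0.67 in months.

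**Does the value of the rate matter?** With λ correctly read as a rate, at assumed values per day:

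| Volume ratio, gap | λ = 0.02 | λ = 0.045 | λ = 0.10 |
|---|---|---|---|
| 1.05, 7 days | 0.667 | 0.865 | 0.951 |
| 1.05, 28 days | 0.933 | 0.980 | 0.997 |
| 1.20, 28 days | 0.734 | 0.921 | 0.987 |

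The first and third rows cross 0.75; the second does not. How often this would happen in this population is unknown.

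**The case against.** The best reply is that this is a slip of wording. The formula, the cut-off and the assignment rule are intact, and no number in the protocol is miscalculated. Section 2.2 never uses the symbol λ, and it gives a modeller everything needed to see that the rate is meant. A literal calculation in days would put every patient in one cohort with PSI near 1, against a preliminary range of 0.03 to 0.75, so the mistake would be hard to miss. The direction of misassignment also depends on the unit: in months the example above falls on the conventional side. Section 2.4 describes both schedules as standards of care with equivalent locoregional control, which limits the harm of a misassignment. Finally, the value of λ may appear in Figure 3, which was not visible in the copy reviewed.

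Most of this stands. It may well be a slip, the harm is conditional, and the sensitivity to λ is a secondary point about clarity that would not carry the finding alone. What does not fall away is that the definition is wrong in both operative sections and is corrected nowhere. Here the label is part of the instruction that allocates treatment, and an allocation rule should be reproducible from the section that states it.

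**Conclusion.** The concern holds: sections 4.1 and 7.1 mislabel λ, and the printed formula equals V/K only with λ = ln2/T_POT. This conclusion is algebraic and rests on no assumed value.

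The size of the effect rests on assumptions: time in days, the illustrative volume ratios, and, for the side-by-side comparison, a lung cancer rate of 0.045 taken as per day. On the literal reading in days the personalisation disappears, because all patients within the stated bounds exceed 0.75. Nothing in the documents shows that PSI was computed that way. It should be fixed because of where it sits. It does not touch the primary test against 49%, the sample size or the power.

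**What to change.** In sections 4.1 and 7.1, define λ as the growth rate per day, λ = ln2/T_POT. Give its value or source next to the formula, unless Figure 3 already does so. Confirm from the records that the PSI values used for assignment were computed with the rate.

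The cost is one phrase in two sections and a check of the recorded PSI values. Fractionation schedules, cut-off, scan window, sample size and power stay as they are. If the rate was used throughout, nothing changes for procedures or patients.
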